4.1 Follow-up Examinations

The subject will have the following study visits / interactions:

- Phone calls at 1 and 2 weeks post-enrollment
- Office visit 4 weeks post-enrollment (Visit 1)
- Phone call 6 weeks after starting levodopa treatment
- Office visit 8 to 10 weeks after starting levodopa treatment (Visit 2)
- Office visit 8 to 12 weeks after stopping levodopa treatment (Visit 3)

Test	Visit / Interaction						
	Baseline	1 week call	2 week call	4 week visit	6 week call	Primary Outcome Visit	Off-Treatment Visit
Telephone call		X	X		X		
Distance acuity each eye*	X			X		X	X
Ocular alignment	X			X		X	X
Titmus Fly	X					X	
Randot Preschool Test	X					X	
Symptom survey	X			X		X	X

*Using Electronic ETDRS acuity testing protocol.

Additional visits are performed at the discretion of the investigator. A form should be completed on the study website for every exam (not just the minimum required exams).

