- 559 • Cylinder power in both eyes must be within 0.50 D of fully correcting the
- 560 astigmatism.
- 561 • Cylinder axis in both eyes is within 6 degrees of the axis in the spectacles when
- 562 cylinder power is ≥ 1.00 D.
- 563 • Myopia of amblyopic eye greater than 0.50 D by spherical equivalent must be
- 564 corrected, and the glasses must not undercorrect the myopia by more than 0.25 D
- 565 or overcorrect it by more than 0.50 D.
- 566 b. Spectacles meeting above criteria must be worn either:
- 567 1) for 16 weeks immediately prior to enrollment, or
- 568 2) until visual acuity in amblyopic eye is stable (defined as two consecutive visual
- 569 acuity measurements by the same testing method at least 4 weeks apart with no
- 570 improvement of more than 4 letters or one logMAR line)
- 571 • An acuity measurement done any of the following ways may be considered the
- 572 first of two consecutive measurements: 1) in current glasses, 2) in trial frames
- 573 with full correction of hypermetropia with cycloplegia, or 3) by having the subject
- 574 return in new glasses for first measurement. *Note: since this determination is a*
- 575 *pre-study procedure, the method of measuring visual acuity is not mandated.*
- 576 6. Ocular examination within 6 months prior to enrollment
- 577 7. Parent available for at least 4 months of follow-up, has home phone (or access to phone),
- 578 and willing to be contacted by clinical site staff and Jaeb Center staff
- 579 8. In the investigator's judgment, the subject is likely to comply with prescribed treatment
- 580 (e.g., no history of poor compliance with patching treatment).

581
582 **2.2.2 Exclusions**

- 583 1. Myopia more than -6.00 D (spherical equivalent) in either eye.

- 584 2. Current vision therapy or orthoptics
585 3. Ocular cause for reduced visual acuity
586 • nystagmus per se does not exclude the subject if the above visual acuity criteria are met
587 4. Prior intraocular or refractive surgery
588 5. History of narrow-angle glaucoma
589 6. Strabismus surgery planned within 16 weeks
590 7. Known allergy to levodopa-carbidopa
591 8. History of dystonic reactions
592 9. Current requirement to take oral iron supplements including multivitamins containing iron
593 during treatment with levodopa-carbidopa
594 10. Current use of antihypertensive, anti-depressant medications, phenothiazines,
595 butyrophenones, risperidone and isoniazid, non-specific monoamine oxidase inhibitors

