3.1 Treatment

Subjects will be prescribed two hours of daily patching plus be randomized to one of two levodopa doses:

- Oral levodopa 0.51 mg/kg/tid with carbidopa 0.17 mg/kg/tid (3 to 1 formulation)
- Oral levodopa 0.76 mg/kg/tid with carbidopa 0.17 mg/kg/tid (approximately 4.5 to 1 formulation)

All subjects will build up to this daily dose over one week with a rapid taper of medication before a primary outcome visit 8 to 10 weeks after starting levodopa/carbidopa treatment. Subjects will continue with the prescribed 2 hours daily patching between the primary outcome visit #2 and the off-treatment visit #3, 8 to 12 weeks after stopping levodopa/carbidopa treatment.

Notes

1. The study will provide patches.
2. A central pharmacy will compound levodopa-carbidopa capsules based upon body weight and ship the study drug to the subject.
3. During the initiation of levodopa-carbidopa therapy, the drugs will be given once daily for three days, twice daily for three days, and three times daily on day 7 of week 1. The drugs will be administered three times daily up until one week prior to the primary outcome visit 8 to 10 weeks after starting treatment.
4. One week prior to the primary outcome visit, the subject will take the drug twice daily for two days, once daily for two days, and then off for three days.
5. Study medications should be administered with meals. For school-age children the midday dose may be given in school if feasible or by administering the midday dose in mid-afternoon after dismissal from school, with the third dose given after dinner.
6. In addition to the study formulation, additional carbidopa may be prescribed at any time to prevent nausea in consultation with the study chair and neurologist serving as the medical monitor, to be paid for by the study.
7. If a subject is noncompliant with treatment, the parents should be encouraged to persist with their efforts to treat to the best of their ability.
8. Prior to deviating from the treatment protocols or prescribing non-protocol treatment, the situation should be discussed with the Protocol Chair.
9. In the case of pregnancy during this study, the levodopa-carbidopa medicine will be discontinued.

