4.1.2 Four-week Visit (Visit 1)

A follow-up visit will occur 4 weeks (± 1 week) following enrollment.

Testing will include the following:

1. Questioning about the occurrence of adverse effects of treatment
2. Completion of symptom survey
3. Evaluation of medication compliance
4. Visual acuity
 - Measured in each eye (right eye first) by a certified examiner using the Electronic ETDRS visual acuity protocol on a study certified visual acuity tester.
5. Ocular alignment at distance and near assessed with the SPCT

775

776 **4.1.3 Primary Outcome Visit (Visit 2)**

777 A primary outcome visit will occur 8 to 10 weeks after starting levodopa treatment, 1 week after
778 beginning the prescribed taper of oral therapy.

779

780 Examination procedures will include the following:

- 781 1. Questioning about the occurrence of adverse effects
782 2. Completion of symptom survey
783 3. Evaluation of medication compliance
784 4. Visual acuity
- 785 • Measured in each eye (right eye first) by a certified examiner using the Electronic
786 ETDRS visual acuity protocol on a study certified visual acuity tester.
- 787 5. Titmus fly and Randot Preschool Stereoacuity test
788 6. Ocular alignment at distance and near assessed with the SPCT

789

790 **4.1.4 Off Treatment Visit (Visit 3)**

791 A follow-up visit will occur 8 to 12 weeks after stopping levodopa treatment.

792

793 Two-hours of prescribed patching should be continued between the primary outcome and off
794 treatment visit. If the visual acuity in the sound eye is reduced by 10 or more letters from
795 baseline at Visit #2, patching can be discontinued.

796

797 Examination procedures will include the following:

- 798 1. Questioning about the occurrence of adverse effects
799 2. Completion of symptom survey
800 3. Visual acuity
- 801 • Measured in each eye (right eye first) by a certified examiner using the Electronic
802 ETDRS visual acuity protocol on a study certified visual acuity tester.
- 803 4. Ocular alignment at distance and near assessed with the SPCT
804

Chapter 5: Miscellaneous Considerations

805
806
807
808
809
810
811
812
813
814
815
816
817
818
819
820
821
822
823
824
825
826
827
828
829
830
831
832
833
834
835
836
837
838
839
840
841
842
843
844
845
846
847
848
849

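### Early side-effect calls and Visit 1 are timed from enrolment while later contacts are timed from drug start or stop, and the 16-week and 4-month entry horizons can end before Visit 3

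*Protocol*

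**What the plan says.** The protocol uses three time origins.

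- **From enrolment:** "Phone calls at 1 and 2 weeks post-enrollment" (Section 4.1, repeated in 1.7 and 4.1.1), and Visit 1: "A follow-up visit will occur 4 weeks (± 1 week) following enrollment" (Section 4.1.2). Section 2.3.4 defines enrolment as completion of the web randomization.
- **From first dose:** "Phone call 6 weeks after starting levodopa treatment" and "Office visit 8 to 10 weeks after starting levodopa treatment (Visit 2") (Section 4.1).
- **From last dose:** "Office visit 8 to 12 weeks after stopping levodopa treatment (Visit 3") (Section 4.1).

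Section 3.1, Note 2 explains why enrolment and first dose can differ: "A central pharmacy will compound levodopa-carbidopa capsules based upon body weight and ship the study drug to the subject". Notes 3 and 4 of the same section bring subjects to three doses a day on day 7 of treatment and leave them off drug for the three days before Visit 2.

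Two entry criteria look ahead over the follow-up period. Section 2.2.1, item 7 requires: "Parent available for at least 4 months of follow-up, has home phone (or access to phone"). Section 2.2.2, item 6 excludes: "Strabismus surgery planned within 16 weeks". Section 6.5.4 counts those 16 weeks from enrolment and cites them in arguing that surgery before the study ends is unlikely. Section 5.2 says that strabismus surgery should not take place during the study.

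**The concern.** Tolerability is a stated objective (Section 1.1), and the week-1 and week-2 calls are the first contacts that ask about nausea, vomiting, headache, fatigue and dyskinesia (Section 4.1.1). The pharmacy needs the body weight, and by inference the randomized arm, before it can compound the assigned capsules. First dose then follows enrolment by some interval. Calls fixed to enrolment drift back towards or before the first dose as that interval grows, and the time on drug at Visit 1 shortens by the same amount. Section 7.1 tabulates the 10-letter response at every visit, so Visit 1 would pool different lengths of exposure.

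The second issue is independent of shipping. Visit 3 is the only assessment more than a few days off drug. Section 1.4 describes loss of acuity gains after stopping levodopa: back to baseline within one week in one study, and by 1.4 lines over about six months in a follow-up report. If the entry horizons are shorter than the time to Visit 3, the criteria admit families who need not be available for it, and children whose surgery is planned for a time when Section 5.2 says it should not be done.

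**Working it through.** **Visit 3, counted from first dose**

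- Visit 2: 8 to 10 weeks = days 56 to 70 (Section 4.1).
- Last dose: three drug-free days earlier (Section 3.1, Note 4), so 56 − 3 = 53 to 70 − 3 = 67.
- Visit 3: 8 to 12 weeks = 56 to 84 days after stopping (Section 4.1).
- Earliest: 53 + 56 = day 109 = 15.6 weeks.
- Mid-window: (63 − 3) + 70 = day 130 = 18.6 weeks.
- Latest: 67 + 84 = day 151 = 21.6 weeks.

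Ignoring the three drug-free days gives 112 to 154 days, or 16.0 to 22.0 weeks. The protocol's 16 weeks is thus reproduced only by the shortest permitted schedule, 8 + 8 weeks.

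**Against the horizons, with no lag**

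The surgery horizon is 16 × 7 = 112 days. Four months is 4 × 365.25 / 12 = 121.75 days, or 17.4 weeks. Counting the four months from enrolment is an assumption, because Section 2.2.1 gives no origin.

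- At mid-window, Visit 3 is 130 − 112 = 18 days past the surgery horizon and 130 − 121.75 = 8.25 days past four months.
- At the latest, it is 151 − 112 = 39 days (5.6 weeks) and 151 − 121.75 = 29.25 days (4.2 weeks) past.
- There are 15 × 29 = 435 permitted day combinations of Visit 2 and Visit 3. Of these, 98% put Visit 3 after 16 weeks and 79% after four months. Equal weighting describes the window and does not forecast actual visit dates.

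Any lag L from enrolment to first dose adds to every figure. At 7 days Visit 3 falls at 16.6 to 22.6 weeks from enrolment, and at 14 days at 17.6 to 23.6 weeks.

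**Early contacts, by lag**

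The lag is not in the protocol; 0 to 14 days is an assumed range. The calls fall on drug days 7 − L and 14 − L, and Visit 1 on days 21 − L to 35 − L.

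| Assumed lag | Week-1 call | Week-2 call | Visit 1 |
|---|---|---|---|
| 0 days | day 7 | day 14 | days 21–35 |
| 7 days | day 0 | day 7 | days 14–28 |
| 14 days | 7 days before first dose | day 0 | days 7–21 |

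Three-times-daily dosing starts on day 7, so the week-2 call precedes it when 14 − L < 7, that is, when the lag exceeds 7 days. Counting the first dosing day as day 1 instead of day 0 moves these figures by one day and does not change the picture.

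**The case against.** Much can be said in the protocol's defence.

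- **The lag may be short.** Section 2.3.4 says not to randomize until the investigator and parent are ready to start, and Section 3.2 treats the calls as one series at weeks 1, 2 and 6. With no lag, the week-2 call comes a week after full dosing begins, and the week-1 call falls at the end of build-up under either clock. This stands in part: the early-call problem is conditional. But readiness to start does not put capsules in hand, and nothing caps the interval.
- **Other contacts cover full-dose tolerability.** Side effects are sought at Visit 1, at the week-6 call and at Visit 2. The decision rules use the proportions completing treatment and stopping for side effects, not answers given in the calls. This stands. A reader might infer that the tolerability decision is undermined, and the protocol does not support that.
- **Surgery is already barred.** Section 5.2 covers the whole study and has any surgery recorded, and Section 6.5.4 also rests on the short treatment phases. A reader might infer that Visit 3 will be confounded by surgery. That goes too far: an instruction against it exists. What remains is that the entry screen admits a child with surgery planned for, say, week 18, which that instruction says should not take place while the child is still in the study.
- **The horizons do not always fall short.** Day 109 lies inside both, and four months is a minimum with no stated origin. This stands, so the claim is that they can end before Visit 3, not that they always do.
- **A dosing record exists.** The daily medication log (Section 3.2) should show when dosing began. This stands, and it makes recording a first-dose date easy.

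**Conclusion.** The point holds in a limited form. The mixed time origins are plain on the page. Their effect on the early calls depends on an unstated lag: none for the week-2 call at zero lag, a call at about the start of full dosing at an assumed 7 days, and no full-dose exposure at either call at 14 days.

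The horizon shortfall needs no assumption about shipping. Visit 3 can fall up to 5.6 weeks after the 16-week surgery horizon and, if four months runs from enrolment, up to 4.2 weeks after the availability minimum, plus any lag. Section 6.5.4's use of 16 weeks as cover to the end of the study holds only for the shortest schedule.

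The primary outcome visit is anchored to first dose, so it, the Table 7-1 rules and the sample size are unaffected. A reader might also infer that the 16-week pregnancy-intention criterion leaves drug exposure uncovered. It does not: the last dose falls on days 53 to 67 (7.6 to 9.6 weeks), so exposure lies inside 16 weeks unless the lag exceeds about six weeks (16 − 9.6 = 6.4).

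**What to change.** 1. In Sections 1.7, 4.1, 4.1.1 and 4.1.2, count the week-1 and week-2 calls and Visit 1 from first dose, as the week-6 call and Visit 2 already are. Record the first-dose date for each subject.
2. Reconcile the availability minimum in Section 2.2.1, item 7 with the latest permitted Visit 3 (21.6 weeks after first dose, plus the lag), and state the date it counts from.
3. Reconcile the surgery statements in Sections 2.2.2, 5.2 and 6.5.4 with each other and with the Visit 3 window. The length of any surgery limit is a clinical matter for the sponsor.

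The cost is wording in a few sections and one date field. A longer availability period might lose a few families who cannot commit to it, which matters a little in a pilot of about 30 subjects.

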4.1.1 Post-enrollment Telephone Calls

Each subject will be contacted by their physician's office via telephone 1 and 2-weeks post-enrollment and again at 6-weeks after starting levodopa treatment. During each call the parent will be questioned about side-effects (nausea, emesis, headache, fatigue, dyskinesias), and reminded of the importance of completing all aspects of the treatment. At the 6-week phone call, parents will be reminded to bring their study medication containers to the primary outcome visit and to taper medication the week before the primary outcome (the subject will take the drug twice daily for two days, once daily for two days and then off for three days).

4.1.2 Four-week Visit (Visit 1)

A follow-up visit will occur 4 weeks (± 1 week) following enrollment.

Testing will include the following:

1. Questioning about the occurrence of adverse effects of treatment
2. Completion of symptom survey
3. Evaluation of medication compliance
4. Visual acuity
 - Measured in each eye (right eye first) by a certified examiner using the Electronic ETDRS visual acuity protocol on a study certified visual acuity tester.
5. Ocular alignment at distance and near assessed with the SPCT

775

776 **4.1.3 Primary Outcome Visit (Visit 2)**

777 A primary outcome visit will occur 8 to 10 weeks after starting levodopa treatment, 1 week after
778 beginning the prescribed taper of oral therapy.

779

780 Examination procedures will include the following:

- 781 1. Questioning about the occurrence of adverse effects
782 2. Completion of symptom survey
783 3. Evaluation of medication compliance
784 4. Visual acuity
- 785 • Measured in each eye (right eye first) by a certified examiner using the Electronic
786 ETDRS visual acuity protocol on a study certified visual acuity tester.
- 787 5. Titmus fly and Randot Preschool Stereoacuity test
788 6. Ocular alignment at distance and near assessed with the SPCT

789

790 **4.1.4 Off Treatment Visit (Visit 3)**

791 A follow-up visit will occur 8 to 12 weeks after stopping levodopa treatment.

792

793 Two-hours of prescribed patching should be continued between the primary outcome and off
794 treatment visit. If the visual acuity in the sound eye is reduced by 10 or more letters from
795 baseline at Visit #2, patching can be discontinued.

796

797 Examination procedures will include the following:

- 798 1. Questioning about the occurrence of adverse effects
799 2. Completion of symptom survey
800 3. Visual acuity
- 801 • Measured in each eye (right eye first) by a certified examiner using the Electronic
802 ETDRS visual acuity protocol on a study certified visual acuity tester.
- 803 4. Ocular alignment at distance and near assessed with the SPCT
804

Chapter 5: Miscellaneous Considerations

805
806
807
808
809
810
811
812
813
814
815
816
817
818
819
820
821
822
823
824
825
826
827
828
829
830
831
832
833
834
835
836
837
838
839
840
841
842
843
844
845
846
847
848
849

5.1 Management of Optical Correction

A refraction should be performed at any time the investigator suspects that refractive error may not be optimally corrected. A change in spectacle correction is at investigator discretion, the cost of which will not be paid for by the study.

5.2 Management of Strabismus

Strabismus surgery should not be done during the study. If performed, surgery will be recorded in the comment section of the Follow-up Examination Form.

5.3 Worsening of Visual Acuity in the Amblyopic Eye

If visual acuity should worsen in the amblyopic eye (or in the sound eye and does not recover with cessation or reversal of treatment), the investigator should evaluate this condition using best clinical judgment and perform whatever work-up is clinically indicated to assess for an alternate cause (i.e., other than amblyopia) for the visual loss. Subjects found to have a cause other than amblyopia that fully explains the visual loss (i.e., amblyopia was never present) will be dropped from the study.

5.4 Subject Withdrawals

A parent or guardian may withdraw a subject from the trial at any time. If the parent or guardian indicates that they want to withdraw the child from the study, the investigator should attempt to speak with them to determine the reason.

The investigator can withdraw the subject if he/she believes that continued participation in the study would be harmful to the subject.

5.5 Subject Payments

The parent/guardian of each subject will be compensated \$30 per visit for completion of the three office visits. If there are extenuating circumstances, additional funds may be provided for travel if expenses exceed \$30 and the subject will be unable to complete the visit without the reimbursement of the travel expenses. All payments will be made by the Jaeb Center by the end of the month following the date of each completed visit.

5.6 Discontinuation of Study

The study may be discontinued by the Steering Committee (with approval of the Data and Safety Monitoring Committee) prior to the preplanned completion of enrollment and follow-up for all subjects.

5.7 Maintaining Subject Follow-up

The Jaeb Center serves as the PEDIG Coordinating Center. The Jaeb Center will be provided with the parent/guardian's contact information. Permission for contacts will be included in the Informed Consent Form. The principal purpose of these contacts will be to help coordinate scheduling of the follow-up examinations.

Chapter 6: Adverse Events

850
851
852
853
854
855
856
857
858
859
860
861
862
863
864
865
866
867
868
869
870
871
872
873
874
875
876
877
878
879
880
881
882
883
884
885
886
887
888
889
890
891
892
893

6.1 Definition

An adverse event is any untoward medical occurrence in a study subject, irrespective of whether or not the event is considered to be treatment-related.

6.2 Recording of Adverse Events

Throughout the course of the study, all efforts will be made to remain alert to possible adverse events or untoward findings. The first concern will be the safety of the subject, and appropriate medical intervention will be made.

The investigator will elicit reports of adverse events from the subject at each visit and complete an adverse event form if necessary. Each adverse event form is reviewed by the Coordinating Center to verify the coding and the reporting that is required.

The study investigator will assess the relationship of any adverse event to be related or unrelated by determining if there is a reasonable possibility that the adverse event may have been caused by the treatment.

The intensity of adverse events will be rated on a three-point scale: (1) mild, (2) moderate, or (3) severe. It is emphasized that the term severe is a measure of intensity: thus, a severe adverse event is not necessarily serious. For example, itching for several days may be rated as severe, but may not be clinically serious.

Adverse events that continue after the subject's discontinuation or completion of the study will be followed until their medical outcome is determined or until no further change in the condition is expected.

6.3 Reporting Serious or Unexpected Adverse Events

A serious adverse event is any untoward occurrence that:

- Results in death
- Is life-threatening; (a non life-threatening event which, had it been more severe, might have become life-threatening, is not necessarily considered a serious adverse event)
- Requires inpatient hospitalization or prolongation of existing hospitalization
- Results in significant disability/incapacity (sight threatening)

Unexpected adverse events are those that are not identified in nature, severity, or frequency in the package insert for levodopa.⁶

Serious or unexpected, related adverse events must be reported to the Coordinating Center immediately via completion of the adverse event form.

The Coordinating Center will notify all participating investigators of any adverse event that is serious, related and unexpected. Notification will be made within 7 days after the Coordinating Center becomes aware of the event.

894
895 Each principal investigator is responsible for informing his/her IRB of serious, unexpected
896 study-related adverse events and abiding by any other reporting requirements specific to their
897 IRB.

898
899 **6.4 Data and Safety Monitoring Committee Review of Adverse Events**

900 A Data and Safety Monitoring Committee (DSMC) will approve the protocol, template informed
901 consent form, and substantive amendments and provide independent monitoring of adverse
902 events. Cumulative adverse event data are semi-annually tabulated for review by the Data and
903 Safety Monitoring Committee (DSMC). Data will be reviewed with the DSMC when 50% of
904 subjects complete the study. Following each DSMC data review, a summary will be provided to
905 IRBs. A list of specific adverse events to be reported to the DSMC expeditiously will be
906 compiled and included as part of the DSMC Standard Operating Procedures document.

907
908 The DSMC Chair will be notified within 24 hours of the coordinating center being notified of a
909 serious adverse event.

910
911 **6.5 Risks**

912
913 **6.5.1 Risks of Examination Procedures**

914 The procedures in this study are part of daily pediatric eye care practice in the United States and
915 pose no known risks. As part of a routine usual-care exam, the subject may receive
916 cycloplegic/dilating eye drops.

917
918 **6.5.2 Side Effects of Treatment**

- 919 1. Patching potentially could decrease the visual acuity in the sound eye, although this is
920 almost always reversible. The diagnosis and management of reverse amblyopia is left to
921 the investigator's judgment- see section 6.5.3.
- 922 2. If skin irritation occurs, the parent will be advised to put an emollient on the skin and
923 discontinue use of the patch for a day. If a skin reaction to the patch or an allergic reaction
924 occurs serious enough to discontinue patching prior to the primary outcome visit (Visit 2),
925 the investigator will call the Protocol Chair to discuss the case. An alternative adhesive
926 patch may be tried. If patching with adhesive patches is discontinued, then the subject
927 should try a Patch Works occluder on glasses (using plano lenses if the subject is not
928 wearing spectacles).
- 929 3. Patching could precipitate the development of an ocular deviation. See Section 6.5.4.
- 930 4. Short courses of 7 to 12 weeks with a dose of 0.51 mg/kg/tid of levodopa-carbidopa (4:1
931 formulation) have been used in the treatment of amblyopia without significant problems
932 (see Chapter 1). Levodopa-carbidopa has been associated with body hypothermia when
933 administered at doses of levodopa 1.02 mg/kg/tid, but not at the lower doses being used for
934 this study. Some children when treated with levodopa for amblyopia have reported
935 headache, emesis, nausea, dry mouth, and fatigue.^{9, 13} Nausea has been lessened by taking
936 the medication with meals, building the dosage up gradually over several days to allow
937 carbidopa levels to reach steady state and administering the lower doses of levodopa. Each
938 of these approaches is being used in this study design.

939 5. Dyskinesias have been found with long-term treatment using levodopa-carbidopa for
940 Parkinson's disease, but not reported with short-term use for amblyopia. Parents will be
941 surveyed at every contact for the onset of dyskinesias. Should they occur, the study
942 medications will be discontinued.

943

944 **6.5.3 Reverse Amblyopia**

945 Patching could decrease the visual acuity in the sound eye, although this is almost always
946 reversible. Reverse amblyopia is unheard of with 2 hours of daily patching in this age group.
947 The diagnosis and management of reverse amblyopia at each of the study visits is left to the
948 investigator's judgment.

949

950 **6.5.4 Development of Strabismus**

951 The study treatment could precipitate the development of a new manifest ocular deviation. If
952 treatment precipitates the development of an ocular deviation (e.g., esotropia), the parent(s) will
953 be advised to have the subject see the investigator as soon as possible. If the development of a
954 new deviation is confirmed on examination, the decision as to whether to continue or discontinue
955 therapy will be left to the investigator.

956

957 If amblyopia treatment is to be discontinued prior to the primary outcome exam, then the
958 Protocol Chair should be called to discuss the situation. The development of a new heterotropia
959 is an accepted risk of standard-care amblyopia therapy. However, previous studies suggest that
960 the resolution of pre-existing strabismus during amblyopia treatment occurs as often as the
961 development of new strabismus. In ATS1, new strabismus occurred in 13% of patching subjects.
962 Twenty-one percent of subjects had resolution of their preexisting strabismus with treatment.²⁹
963 In ATS3 there was no increase in the proportion of subjects with strabismus with patching for
964 teens 13 to <18 years, and with patching plus atropine for children 7 to <13 years.¹ In ATS9
965 there was no increase in the proportion of subjects with strabismus following 2 hours daily
966 patching.² The risk of strabismus in this study is no greater than it would be with standard care
967 of amblyopia.

968

969 In view of the short duration of the treatment phases of the study and the eligibility criterion that
970 strabismus surgery is not planned in the 16 weeks following enrollment, it is unlikely that
971 strabismus surgery will need to be performed prior to the end of the study.

972

973 **6.6 Risk Assessment**

974 This protocol falls under DHHS 46.405, which is a minor increase over minimal risk. In
975 addition, it is the belief of the investigators that this study also presents prospect of direct benefit
976 to the subjects and general benefit to others with amblyopia.

977

Chapter 7: Statistical Considerations

978
979
980
981
982
983
984
985
986
987
988
989
990
991
992
993
994
995
996
997
998
999
1000
1001
1002
1003
1004
1005
1006
1007
1008
1009
1010
1011
1012
1013
1014
1015
1016
1017
1018
1019

